8.10.6.2. Myocarditis/Pericarditis

A case of suspected, probable, or confirmed myocarditis, pericarditis, or myopericarditis should be reported as an AESI, even if it does not meet criteria per the CDC Working Case Definitions. The event should also be reported as an SAE if it meets seriousness criteria (see Section 8.9.8).

An independent Cardiac Event Adjudication Committee (CEAC) will review suspected cases of myocarditis, pericarditis, and myopericarditis to determine if they meet CDC criteria for “probable” or “confirmed” events (Section 8.11.2).

The CDC Working Case Definitions are provided in Section 11.5 as guidance.

8.10.7. Assessment of Intensity/Severity

An event is defined as “serious” when it meets at least one of the predefined outcomes as described in the definition of an SAE (Section 8.9.8), NOT when it is rated as severe.

The severity (or intensity) of an AR or AE refers to the extent to which it affects the participant’s daily activities. The Toxicity Grading Scale for Healthy Adult and Adolescent Volunteers Enrolled in Preventative Vaccine Clinical Trials (DHHS 2007) will be used to categorize local and systemic reactogenicity events (solicited ARs), clinical laboratory test results, and vital sign measurements observed during this study. Specific criteria for local and systemic reactogenicity events are presented in Section 8.10.3.

The determination of severity for all unsolicited AEs should be made by the Investigator based upon medical judgment and the definitions of severity as follows:

- Mild: These events do not interfere with the participant’s daily activities.
- Moderate: These events cause some interference with the participant’s daily activities and require limited or no medical intervention.
- Severe: These events prevent the participant’s daily activity and require intensive therapeutic intervention.

Study staff should elicit from the participant the impact of AEs on the participant’s activities of daily living to assess severity and document appropriately in the participant’s source documentation. An AE characterized as intermittent requires documentation of onset and duration of each episode. An AE that fluctuates in severity during the course of the event is reported once in the eCRF at the highest severity observed.

8.10.8. Assessment of Causality

The Investigator will assess causality (ie, whether there is a reasonable possibility that the study intervention caused the event) for all AEs and SAEs. The relationship will be characterized using the following classification:

Not related: There is not a reasonable possibility of a relationship to the study intervention. Participant did not receive the study intervention OR temporal sequence of the AE onset relative to administration of the study intervention is not reasonable OR the AE is more likely explained by another cause than the study intervention.

Related: There is a reasonable possibility of a relationship to the study intervention. There is evidence of exposure to the study intervention. The temporal sequence of the AE onset relative to the administration of the study intervention is reasonable. The AE is more likely explained by the study intervention than by another cause.

8.11. Safety Oversight

8.11.1. Data and Safety Monitoring Board

A DSMB will be used throughout the conduct of this study. This committee will be composed of independent members with relevant therapeutic and/or biostatistical expertise to allow for the ongoing review of safety data from this study population. Safety data will be reviewed according to intervals defined in the DSMB charter and will also occur as needed.

8.11.2. Independent Cardiac Event Adjudication Committee

An independent Cardiac Event Adjudication Committee (CEAC) of medically qualified personnel, including cardiologists, will review suspected cases of myocarditis and pericarditis to determine if they meet CDC criteria of “probable” or “confirmed” events, and to assess severity ([Gargano et al 2021](#)). Any cases that the CEAC assesses as representing probable or confirmed cases of myocarditis or pericarditis will be referred to the Sponsor, who will then make a final decision on whether to suspend further enrollment and/or study dosing based on an assessment of the overall potential risk to study participants.

The CEAC will operate under the rules of an approved charter that will be written and reviewed at the organizational meeting of the CEAC. Details regarding the CEAC composition, responsibilities, procedures, and frequency of data review will be defined in its charter.

8.12. Treatment of Overdose

As the study intervention is to be administered by a HCP, it is unlikely that an overdose will occur.

However, in the event of an overdose, the Investigator should:

1. Contact the Medical Monitor immediately.
2. Closely monitor the participant for any AE/SAE and laboratory abnormalities until the last safety follow-up visit.
3. Report any signs or symptoms associated with the overdose as an AE and record details in the relevant AE/SAE sections in the eCRF.
4. Document the quantity of the excess dose in the eCRF.

8.13. Pharmacokinetics

Pharmacokinetic parameters are not evaluated in this study.

8.14. Pharmacodynamics

Pharmacodynamic parameters are not evaluated in this study.

8.15. Biomarkers

Additional biomarkers may be evaluated as part of future research objectives and development. Biomarker assessments may be evaluated as part of the study, which may include serum antibody levels, genomic and transcriptomics studies from consented participants.

According to the ICF ([Section 11.1.6](#)), serum from biomarker testing may be used for future research, which may be performed at the discretion of the Sponsor to further characterize the immune response to influenza vaccines, additional assay development, and the immune response across influenza viruses ([Section 11.1.10](#)). Optional blood collections for DNA and mRNA sequencing may be performed to research connections between vaccine responses and safety.

NP swabs collected in the study may be used for assay development purposes.

8.16. Patient-Reported Outcomes and Medical Resource Utilization

Exploratory objectives related to patient-reported outcomes (PROs) and medical resource utilization are listed in [Section 3](#).

Patient-reported outcomes and medical resource utilization associated with symptoms of ILI will be assessed at time points specified in the SoE ([Table 1](#)).

8.16.1. Patient-reported Outcome Measures

Patient-reported outcome measures will include the following questionnaires: EFS, EQ-5D-5L scale, and WPAI:ILI.

8.16.1.1. EFS

At Day 1, the EFS will be collected by clinical staff for participants aged 65 years and older. This scale is a brief, valid, and reliable tool for assessment of frailty across 9 domains: cognition, general health status, functional independence, social support, medication use, nutrition, mood, continence, and functional performance.

8.16.1.2. EQ-5D-5L

The EQ-5D-5L consists of both the EQ-5D descriptive system and the EQ visual analogue scale.

For all participants, responses to the EQ-5D-5L will be collected using the eDiary at Day 1 (baseline), Day 91, Day 181, Day 271, and Day 361 (Month 12)/EoS. For participants reporting symptoms of ILI, the EQ-5D-5L responses will be collected using the eDiary on the day of symptoms reporting (+1 day), and 5 days (+1 day) later.

8.16.1.3. WPAI

For participants reporting symptoms of ILI, the WPAI over the previous 7 days will be collected using the eDiary at 5 days (+1 day) following start of the symptoms. The participant will be prompted to report productivity or activity impairment related to their ILI. The list of the ILI symptoms that are part of their reporting of symptoms are the specific health problem to be considered.

8.16.2. Medical Resource Utilization

8.16.2.1. Hospitalization

For hospital stay (new hospitalization or prolongation of existing hospital stay), the following information will be collected for confirmed influenza cases from SAE and MAAE reports:

- Admission date
- Discharge date
- Intensive care unit stay (yes or no)

8.16.2.2. Outpatient Medical Resource Utilization

For participants reporting MAAEs, outpatient medical resource utilization will be collected, where available. Options that will be provided are: outpatient/physician visit; emergency room/urgent care visit; and telemedicine visit.

9. STATISTICAL CONSIDERATIONS

9.1. Blinding and Responsibility for Analyses

This is an observer-blind study. The Investigator, clinic staff, study participants, site monitors, and Sponsor personnel (or its designees) will be blinded to the study intervention administered until the study database is locked and unblinded, with the following exceptions:

- Unblinded personnel (of limited number) will be assigned to vaccine accountability procedures and will prepare the study intervention for all participants. These personnel will have no study functions other than the study intervention management, documentation, accountability, preparation, and administration. They will not be involved in participant evaluations and will not reveal the identity of the study intervention to either the participant or the blinded clinic personnel involved in the conduct of the study unless this information is necessary in the case of an emergency.
- Unblinded clinic personnel will administer the study intervention. They will not be involved in assessments of any study endpoints.
- Unblinded site monitors, not involved in other aspects of monitoring, will be assigned as the study intervention accountability monitors. They will have responsibilities to ensure that sites are following all proper study intervention accountability, preparation, and administration procedures.
- An independent unblinded statistical and programming team will perform the preplanned interim analyses ([Section 9.5.4](#)). Sponsor team members will be pre-specified to be unblinded to the interim analyses results and will not communicate the results to the blinded Investigators, clinic staff, clinical monitors, or participants.
- The DSMB may review data, as appropriate, to safeguard the interests of clinical trial participants and to help ensure the integrity of the study.

The dosing assignment will be concealed by having the unblinded pharmacy personnel prepare the study intervention in a secure location that is not accessible or visible to other clinic staff. An opaque sleeve over the syringe used for injection will maintain the blind at the time of injection, as mRNA-1010 will look different from the active comparator. Only delegated unblinded clinic staff will conduct the injection procedure. Once the injection is completed, only the blinded clinic staff will perform further assessments and interact with the participants. Access to the randomization code will be strictly controlled at the pharmacy.

Procedures for breaking the blind in the case of a medical emergency are provided in [Section 6.3.7](#).

9.2. Statistical Hypotheses

The primary efficacy objective of this study is to evaluate relative vaccine efficacy (rVE) of mRNA-1010 as compared to an active comparator, to prevent the occurrence of the first episode of RT-PCR confirmed protocol-defined ILI caused by any influenza A or B virus strains.

The null hypothesis to be tested first is that the rVE of mRNA-1010 as compared to an active comparator is inferior, using a 10% noninferiority margin (NIM), (ie, $H_0^1: rVE \leq -10\%$). The rVE

is defined as the percent of reduction in the hazards of the primary endpoint (mRNA-1010 vs. active comparator). Equivalently, the null hypothesis is: H_0^1 : hazard ratio (HR) ≥ 1.1

A stratified Cox proportional hazard model will be used to assess the HR between mRNA-1010 and the active comparator at a 1-sided 2.5% significance level, using the PP Set.

The trial will be considered to meet the primary efficacy objective by demonstrating noninferiority (NI) of mRNA-1010 to the active comparator if the *p-value* for rejecting $HR \geq 1.1$ is less than the nominal *p-value* based on the Lan-DeMets Pocock approximation spending function at the IA or final analysis, on the PP Set. Cases will be counted starting 14 days after the vaccination.

Once NI is demonstrated, the rVE will be further evaluated using the same endpoint for superiority. The null hypothesis to be tested is H_0^2 : rVE $\leq 0\%$. Equivalently, the null hypothesis is: H_0^2 : HR ≥ 1 .

Superiority of mRNA-1010 versus (vs.) the active comparator on the primary efficacy endpoint will be concluded if the *p-value* for rejecting $HR \geq 1$ is less than the nominal *p-value* based on the Lan-DeMets Pocock approximation spending function, on the mITT Set.

9.3. Sample Size

The sample size is driven by the total number of cases to demonstrate rVE (mRNA-1010 vs. active comparator) to prevent the first episode of RT-PCR confirmed protocol-defined ILI caused by any influenza A or B virus strains.

Under the assumption of proportional hazards and with 1:1 randomization of mRNA-1010 and active comparator, a total of 365 cases on the PP Set will provide at least 93% power to establish a NI claim with a selected NIM = 10%, ie, rejecting the null hypothesis H_0^1 : rVE $\leq -10\%$, with one IA using the Lan-DeMets Pocock boundary for efficacy and a log-rank test statistic with an overall 1-sided Type I error rate of 2.5%.

The number of cases will be continuously monitored using external epidemiologic data (eg, CDC.gov). It is projected that by middle of February 2023, approximately 274 cases (75% of the targeted cases) will be observed in the PP Set. In the scenario that fewer cases are observed by middle of February, the IA will still be conducted around this timeframe because of the seasonality of influenza in the Northern Hemisphere, and the nominal alpha to be spent that the IA and final analysis will be adjusted accordingly.

The total number of cases pertains to the PP Set accruing at least 14 days after study intervention.

Approximately 23,000 participants will be randomized with the following assumptions:

- The target rVE of mRNA-1010 to the active comparator is 25% to prevent the first episode of RT-PCR confirmed protocol-defined ILI caused by any influenza A or B virus strains.
- An attack rate of 2% in the active comparator for the primary endpoint.
- One IA in the middle of February 2023 with approximately 75% of total target cases expected across 2 study intervention groups in the PP Set.

- A dropout rate ~ 10% (not evaluable for the PP Set).
- Type I error rate will be adjusted using the Lan-DeMets Pocock boundary.

If the IA is conducted exactly at 75% of total target cases, the nominal 1-sided Type I error rate will be 2.07% at IA and 1.2% at final analysis for NI testing, respectively.

Once NI is demonstrated, the rVE will be further evaluated for superiority of mRNA-1010 over the active comparator. The planned sample size (23,000 participants) is expected to generate approximately 386 cases in the mITT Set and will provide approximately 76% power to support the superiority claim with the following assumptions:

- The target rVE of mRNA-1010 to the active comparator is 25% to prevent the first episode of RT-PCR confirmed protocol-defined ILI caused by any influenza A or B virus strains.
- An attack rate of 2% in the active comparator for the primary endpoint.
- An IA in the middle of February 2023 with approximately 290 cases expected (75% of total target cases) across 2 study intervention groups in the mITT Set (defined in [Section 9.4](#)).
- A dropout rate ~ 4% (not evaluable for the mITT Set).
- Type I error rate will be adjusted using the Lan-DeMets Pocock boundary.

The total number of cases pertains to the mITT Set accruing at least 14 days after the study intervention. If the IA is conducted exactly at 75% of total target cases, the nominal 1-sided Type I error rate will be 2.07% at IA and 1.2% at final analysis, respectively.

The sample size and power calculations are based on the log-rank test for a survival endpoint using the EAST software (version 6.5.2).

9.4. Analyses Populations

Table 6: Populations for Analyses

Analysis Sets	Description
Randomization Set	All participants who are randomized, regardless of the participants' treatment status in the study.
Full Analysis Set (FAS)	All randomized participants who received any study intervention. Participants will be analyzed according to the group to which they were randomized.
Modified Intent-to-Treat Set (mITT)	All participants in the FAS except those who discontinued from the study prior to 14 days following administration of study intervention. The mITT Set will be used as the primary analysis set for efficacy endpoints evaluating superiority. Participants will be analyzed according to the group to which they were randomized.
Per-Protocol (PP) Set	All participants in the mITT, excluding those with significant protocol deviations that could adversely impact efficacy (eg, disease or

Analysis Sets	Description
	
therapeutic intervention that might cause suboptimal response to the study intervention). The PP Set will be used as the primary analysis set for efficacy endpoints evaluating noninferiority.
 
Participants will be analyzed according to the group to which they were randomized.

Immunogenicity Subset	
All participants in the biomarker subset who are in the FAS and have baseline and Day 29 antibody assessment via HAI assay.
 
Participants will be analyzed according to the group to which they were randomized.

PP Immunogenicity Subset	
The PP Immunogenicity Subset includes all participants in the Immunogenicity Subset who received the planned dose of IP, complied with the immunogenicity testing schedule, and had no major protocol deviations that impact the immunogenicity assessment. Participants with RT-PCR–confirmed influenza between Days 1 to 29 will be removed from the PP Immunogenicity Set.
 
The PP Immunogenicity Set will be used for all analyses of immunogenicity unless specified otherwise.
 
Participants will be analyzed according to the group to which they were randomized.

Solicited Safety Set	
The Solicited Safety Set consists of all randomized participants who received any study intervention and contributed to any solicited adverse reaction (AR) data.
 
The Solicited Safety Set will be used for the analyses of solicited ARs and participants will be included in the vaccination group corresponding to the study intervention that they actually received.

Safety Set	
All randomized participants who received any study intervention. The Safety Set will be used for all analyses of safety except for the solicited ARs, and participants will be included in the vaccination group corresponding to the study intervention that they actually received.

9.5. Statistical Analyses

This section is a summary of the planned statistical analyses of the primary and secondary endpoints.

The overall Type I error rate for the primary endpoint at the IAs and the final analysis is strictly controlled at 2.5% (1-sided) based on the Lan-DeMets Pocock spending function (see [Section 9.6](#) for details). The primary efficacy results that will be considered statistically significant after consideration of the strategy for controlling the Type I error is described in [Section 9.5.1](#). Statistical significance of the primary efficacy endpoint for the primary objective can be achieved at either IA or at the final analysis.

A sequential/hierarchical testing procedure will be used to control Type I error rate over the primary efficacy objective (endpoint) and secondary efficacy objectives (endpoints). Secondary

efficacy objectives (endpoints) will only be tested at the planned IA or final analysis, whichever is applicable, when the primary efficacy endpoint for the primary objective achieves statistical significance. In that case, refer [Section 9.6.2](#) for the multiplicity adjustments among the efficacy objectives (endpoints).

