9.6.2. Multiplicity

To control the overall Type I error for the study, a hierarchical testing strategy will be used to test the primary and secondary efficacy endpoints (Figure 1).

Figure 1: Testing Sequence of the Primary and Secondary Endpoints

Noninferiority of mRNA-1010 vs. the active comparator on the primary efficacy endpoint will be declared if the *p-value* for rejecting $HR \geq 1.1$ is less than the nominal *p-value* based on the Lan-DeMets Pocock approximation spending function, on the PP Set. The nominal alpha levels (1-sided) are 2.07% at IA and 1.2% at the final analysis, respectively, if the IA is conducted when 75% of total target cases are accumulated across the 2 groups.

Once the NI criteria is met for the primary efficacy endpoint, superiority of mRNA-1010 relative to the active comparator will be tested on the mITT Set. The superiority of rVE will be considered demonstrated if the *p-value* for rejecting $HR \geq 1$ is less than the nominal *p-value* based on the Lan-DeMets Pocock approximation spending function, on the mITT Set. For this superiority testing, the nominal 1-sided alpha level will be 2.07% at the planned IA and at 1.2%

at final analysis, respectively, if the IA is conducted when 75% of total target cases are accumulated across the 2 groups.

If the above superiority is demonstrated, then the following secondary efficacy endpoints will be evaluated for NI and superiority in the order outlined in [Figure 1](#) at the final analysis using 1-sided 2.5% Type I error rate:

- rVE of mRNA-1010 vaccine vs the active comparator against the first episode of RT-PCR confirmed protocol-defined ILI caused by influenza A or B strains with similarity to the vaccine strains.
- rVE of mRNA-1010 vaccine vs the active comparator against the first episode of RT-PCR–confirmed protocol-defined ILI caused by influenza A or B antigenically matched influenza A or B strains.

The testing sequence can only continue to the next level only if all tests at the higher level achieve statistical significance at the 1-sided 2.5% alpha level. If a test at the higher level fails to demonstrate statistical significance, then the testing sequence will stop, and all testing thereafter will not be conducted.

Analyses of other remaining secondary efficacy endpoints are not controlled for multiplicity.

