In addition to the information presented in the statistical considerations section of the protocol (Section 9) which provides the principal features of analyses for this study, this SAP provides statistical analysis details and data derivations. It also documents modifications or additions to the analysis plan which are not “principal” in nature and result from information that was not available at the time of protocol finalization. If the methods in this SAP differ from the methods described in the protocol, the SAP will prevail.

Study mRNA-1010-P302 is a Phase 3, randomized, observer-blind, active-controlled study to evaluate the safety and efficacy of mRNA-1010 candidate seasonal influenza vaccine as compared with an active comparator in adults ≥ 50 years of age.

Parexel Biostatistics and programming team, designee of Moderna Biostatistics and Programming department, will perform the statistical analysis; Statistical Analysis System (SAS) Version 9.4 or higher will be used.

In this document, injection of investigational product (IP), injection, vaccination, and dose are used interchangeably; vaccination group and treatment group are used interchangeably.

2. Study Objectives

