4.5. Blinding and Unblinding

This is an observer-blind study. The Investigator, clinic staff, study participants, site monitors, and Sponsor personnel (or its designees) will be blinded to the study intervention administered until the study database is locked and unblinded, with the following exceptions:

- Unblinded personnel (of limited number) will be assigned to vaccine accountability procedures and will prepare the study intervention for all participants. These personnel will have no study functions other than the study intervention management, documentation, accountability, preparation, and administration. They will not be involved in participant evaluations and will not reveal the identity of the study intervention to either the participant or the blinded clinic personnel involved in the conduct of the study unless this information is necessary in the case of an emergency.
- Unblinded clinic personnel will administer the study intervention. They will not be involved in assessments of any study endpoints.
- Unblinded site monitors, not involved in other aspects of monitoring, will be assigned as the study intervention accountability monitors. They will have responsibilities to ensure that sites are following all proper study intervention accountability, preparation, and administration procedures.
- An independent unblinded CRO statistical and programming team will perform the preplanned interim analyses and final analysis. The unblinded CRO statistical team will not be involved in either study design or the regular study conduct.
- Should the planned IA or the final analysis result in the Sponsor's decision to file regulatory submissions, a designated Sponsor team may be unblinded to prepare regulatory submissions. Once unblinded, the unblinded sponsor team will not be involved in the regular study conduct or communicate the unblinded results to the blinded Sponsor personnel, Investigators, clinic staff, clinical monitors or study participants. A separate blinded Sponsor team will carry out the study conduct

through the end of study when all participants have completed the month-12 follow-up or have withdrawn from the study.

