6.3.2. Analysis of the Key Secondary Efficacy Endpoints

A sequential/hierarchical statistical multiple testing procedure will be used to control the overall Type 1 error rate over the primary efficacy endpoint and key secondary efficacy endpoints.

Key secondary efficacy endpoints will only be tested for NI and superiority at the final analysis using one-sided 2.5% Type I error rate when the primary efficacy endpoint achieves statistical significance. See [Section 6.6](#) for the multiplicity adjustments among the primary efficacy endpoint and the key secondary efficacy endpoints.

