The IA will occur with data cut-off around the middle of February in 2023 when approximately 75% of the total cases in the PP Set are expected to be observed. The study will be considered positive (non-inferior) at IA if the one-sided p-value for rejecting $HR \geq 1.1$ is less than 2.07% based on the Lan-DeMets Pocock approximation spending function, provided that IA is conducted exactly at the 75% information fraction. The nominal alpha to be spent at the IA and final analysis may be adjusted according to the actual number of cases observed at IA.

If NI is demonstrated at IA, the superiority claim in the same primary endpoint will be evaluated to support the primary objective, i.e., H_0^2 : $HR \geq 1$ (equivalently, $rVE \leq 0\%$). Approximately 290 cases are expected to be observed in the mITT Set at IA. Superiority of mRNA-1010 relative to the active comparator is demonstrated if the one-sided p-value for rejecting $HR \geq 1$ (equivalently, $rVE \leq 0\%$) is less than 2.07% based on the Lan-DeMets Pocock approximation spending function. The nominal alpha to be spent at the IA and final analysis may be adjusted according to the actual number of cases observed at IA.

No formal statistical testing is planned at the IA for key secondary and other secondary efficacy endpoints. However, descriptive summarizations and statistical analyses may be conducted in an exploratory manner to support the primary endpoint.

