6.6. Multiplicity Adjustment

To control the overall one-sided Type I error rate for the study, a hierarchical testing strategy will be used to test the primary and secondary efficacy endpoints ([Figure 1](#)).

Figure 1: Testing Sequence of the Primary and Secondary Endpoints

Noninferiority of mRNA-1010 vs. the active comparator on the primary efficacy endpoint will be declared if the one-sided p-value for rejecting $HR \geq 1.1$ is less than the nominal alpha based on the Lan-DeMets Pocock approximation spending function, based on the PP Set. The nominal alpha levels (one-sided) are 2.07%, and 1.2% at the IA and final analysis,

respectively, if the IA is conducted when 75% of total target cases are accumulated across the 2 groups.

If the NI criteria is met for the primary efficacy endpoint, superiority of mRNA-1010 relative to the active comparator will be tested on the mITT Set. The superiority of rVE will be demonstrated if the one-sided p-value for rejecting $HR \geq 1$ is less than the nominal alpha based on the Lan-DeMets Pocock approximation spending function, based on the mITT Set. For this superiority testing, the nominal one-sided alpha level will be 2.07% and 1.2% at the planned IA and final analysis, respectively, if the IA is conducted when 75% of total target cases are accumulated across the two treatment groups.

If the above superiority is demonstrated, then the following secondary efficacy endpoints will be evaluated for NI and superiority in the order outlined in [Figure 1](#) at the final analysis using a one-sided 2.5% Type I error rate:

- rVE of mRNA-1010 vs. the active comparator against the first episode of RT-PCR confirmed protocol-defined ILI caused by influenza A or B virus strains with similarity to the seasonal influenza vaccine strains.
- rVE of mRNA-1010 vs. the active comparator against the first episode of RT-PCR confirmed protocol-defined ILI caused by influenza A or B virus strains antigenically matched to the seasonal influenza vaccine strains.

The testing sequence can only continue to the next level if all tests at the higher level achieve statistical significance at the 2.5% alpha level. If a test at the higher level fails to demonstrate statistical significance, then the testing sequence will stop, and all testing thereafter will not be conducted.

Analyses of other remaining secondary efficacy endpoints are not controlled for multiplicity.

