6.8. Data Safety Monitoring Board

A DSMB will be used throughout the conduct of this study. This committee will be composed of independent members with relevant therapeutic and/or biostatistical expertise

to allow for the ongoing review of safety data from this study population. Safety data will be reviewed according to intervals defined in the DSMB charter and will also occur as needed.

The DSMB will review the IA results and make recommendations to the Sponsor in terms of study results reporting and unblinding based on the boundaries of early efficacy as described in this SAP.

The Sponsor may also request that the DSMB conduct ad hoc reviews of safety events from this study. The DSMB composition, its remit, and frequency of data review will be further defined in the DSMB charter.

7. Changes from Planned Analyses in Protocol

No changes have been made to those analyses planned in the protocol.

8. References

Department of Health and Human Services (DHHS), Food and Drug Administration (FDA), Center for Biologics Evaluation and Research (US). Guidance for industry: Toxicity grading scale for healthy adult and adolescent volunteers enrolled in preventative vaccine clinical trials. September 2007.

Available from:

<https://www.fda.gov/downloads/BiologicsBloodVaccines/GuidanceComplianceRegulatoryInformation/Guidances/Vaccines/ucm091977.pdf>.

9. List of Appendices

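### Does the plan leave open whether the key secondary endpoints are formally tested at the interim analysis or only at the final?

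*Protocol*

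**What the plan says.** Protocol Section 9.5, which introduces itself as a summary, says that secondary efficacy endpoints "will only be tested at the planned IA or final analysis, whichever is applicable", on condition that the primary endpoint is significant. Its next sentence refers to Section 9.6.2 for the multiplicity adjustments.

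Protocol Section 9.6.2 takes the two key secondary endpoints (strains similar to the vaccine, then antigenically matched strains) and tests them for noninferiority (NI) and superiority "at the final analysis using 1-sided 2.5% Type I error rate", after primary superiority has been shown.

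The SAP agrees with 9.6.2:
- Section 6.3.2: "Key secondary efficacy endpoints will only be tested for NI and superiority at the final analysis".
- Section 6.5.1: "No formal statistical testing is planned at the IA for key secondary and other secondary efficacy endpoints". Descriptive work at the IA is allowed as exploratory.
- Sections 6.5.2 and 6.6 repeat the final-only timing at one-sided 2.5%.

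The gate sentence in SAP 6.6 lets testing proceed only if "all tests at the higher level achieve statistical significance at the 2.5% alpha level"; protocol 9.6.2 has the same rule. Just above it, both documents give the nominal levels for primary NI and superiority: 2.07% at the IA and 1.2% at the final, if the IA falls at 75% of cases.

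On precedence, SAP Section 1 says: "If the methods in this SAP differ from the methods described in the protocol, the SAP will prevail". SAP Section 7 records: "No changes have been made to those analyses planned in the protocol".

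**The concern.** Read alone, the 9.5 clause suggests that primary success at the IA opens formal secondary testing at the IA. No passage assigns a level to such a test. SAP Section 4.5 also foresees that, if the IA or the final analysis leads to the Sponsor's "decision to file regulatory submissions, a designated Sponsor team may be unblinded to prepare regulatory submissions". A filing after a positive IA could then carry key secondary results that are confirmatory under protocol 9.5 and exploratory under SAP 6.5.1.

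The gate sentence seems to add to this. It gives a single 2.5% level and names no look, although the primary tests above it are judged at 2.07% and 1.2%. A literal reader might accept a final primary p-value between 1.2% and 2.5% as opening the gate.

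At stake would be the type I error of the two key secondary claims, and whether someone could choose between the readings after seeing IA results.

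**Working it through.** **1. Reproduce the plan's boundaries.** Inputs are overall one-sided alpha 2.5%, Pocock-type Lan-DeMets spending, and information fraction t = 0.75 (protocol 9.3 and Table 8).

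- IA: 0.025 × ln(1 + (e − 1) × 0.75) = 0.0207, z = 2.0395. The plan states 2.07%.
- Final: solving P(Z₁ > 2.0395 or Z₂ > c) = 0.025 with correlation √0.75 gives c = 2.2582, nominal 0.0120. The plan states 1.2%.
- NI at the IA, 274 cases, hazard ratio (HR) 0.75 against 1.1: drift (√274/2) × ln(1.1/0.75) = 3.17, so P(Z > 2.0395) = 87.1%. Cumulative power is 93.7%. Both match protocol Table 8.
- Superiority at the IA, 290 cases: drift (√290/2) × ln(1/0.75) = 2.45, giving 65.9%. Cumulative power is 76.4%; the plan states about 76%.

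**2. How often the question could arise.** At true relative vaccine efficacy (rVE) 25% and 75% information, the gate opens at the IA in about 66% of trials. With 290 cases this falls to 44% at rVE 20% and 26% at rVE 15%. The IA date is fixed by calendar, so the case count may also differ.

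**3. Type I error for one key secondary hypothesis under its null.**

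| Reading | Error |
|---|---|
| One test at the final, 2.5% (protocol 9.6.2 and SAP) | at most 2.5% |
| One test, at whichever look the primary succeeds, true rVE 25% | 2.51%–2.54% (simulated) |
| Tests at both looks, 2.5% each, t = 0.75 | 3.67% |

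The first row needs no simulation. A false claim requires p < 2.5% at one fixed test, and conditioning on an open gate can only reduce that probability. It does not matter whether the gate opened at the IA or the final.

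The second row assumes that key secondary cases are 30%–90% of primary cases, since the documents give no figure. The error can reach 2.9% with a 90% share, but only when the primary effect is weak. Near HR 0.95 the drift at the IA is (√290/2) × ln(1/0.95) = 0.44, and superiority is met there in only about 5% of trials. So 2.9% and the 66% in step 2 belong to different truths. A 90% share is in fact impossible at HR 0.75 for a key secondary with HR 1: with comparator rate 1 and mRNA-1010 rate 0.75, such cases can be at most 0.75 per arm, a share of 1.5/1.75 = 86%.

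The third row needs two unadjusted tests. Section 9.5 offers one look or the other, and no section plans both.

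**4. The gate sentence.** Each primary test has its success criterion in the paragraphs just before it, by look. Protocol 9.5 gives 2.5% as the overall one-sided level across looks. Read together, 2.5% is the overall level of each test in the sequence, and a final primary p of 1.2%–2.5% without IA success is a failure that stops testing.

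**The case for a change.** The strongest case for acting is that the conflict lies inside the protocol itself, between 9.5 and 9.6.2, so the SAP's precedence clause is not the whole answer. Section 9.5 states its own timing before it points to 9.6.2, and the pointer concerns multiplicity adjustments. SAP Section 1 describes its departures from the protocol as not principal in nature, while the look at which a confirmatory hypothesis is tested arguably is principal. SAP Section 7 lists no difference. Repair would take a few words, and would best be done before unblinded results exist.

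The wording conflict stands: the 9.5 clause is loose. The rest carries little weight. The section that sets out the testing sequence is 9.6.2, it names the look and the level, and 9.5 defers to it. The SAP follows 9.6.2, so measured against the protocol's operative section its statement of no changes is accurate. The status of key secondary results in a filing after the IA is not open either, because SAP 6.5.1 makes them exploratory. The final-only rule is already written in both documents, so following it after the IA would not be a choice made with results in hand.

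**Conclusion.** No change follows. The clause in protocol 9.5 is a clerical slip in a summary paragraph. Protocol 9.6.2 and four SAP sections give one consistent rule: each key secondary hypothesis is tested once, at the final analysis, at one-sided 2.5%. That rule holds the error at 2.5% or less, and this does not depend on the information fraction at the IA, the true primary effect or the share of key secondary cases. Aligning the clause would tidy the text and leave every boundary, power figure, case count and conclusion as it is. The larger error figures rest on tests the plan does not schedule or on primary effects well below the design value. The conclusion assumes that analysts follow the specific multiplicity section and the SAP, as both documents direct. Figure 1 is not reproduced in the text reviewed; both documents cite it for the order of testing.
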